6.2. Missing Assessments

All data will be listed as collected. Descriptive statistics will be calculated on the data collected without replacement. For time to event, analysis data will be censored.

Missing and partial dates will be replaced as described in Section [6.1](#).

While it is possible that some patients will have missing or partial date information for SAEs or other safety data collections, analyses of the safety endpoints will include all patients in the Safety Population, unless specifically stated otherwise.

Missing data might be present for the analyses of the clinical laboratories and vital signs (eg, where the parameter was not measured at a required time points, which are the dates of treatment switch), and PROs. In many situations, there will often be other measurements of the parameter within a time frame that is applicable eg. during each treatment period. In such cases, the closest measurement to the switch time point within the treatment period will be used for analysis (Section 11). If such a measurement does not exist, then the patient will be excluded from the analysis of that variable at that timepoint. If 2 measurements are equidistant from the scheduled time point, the first one will be used.

Estimated GFR and LVMi data will be used as is and the actual time of the measurement will be utilized in the analysis. Analysis of LVMi will be exploratory.

7. STATISTICAL ANALYSIS CONSIDERATIONS

7.1. Conventions

Unless otherwise noted, data will be summarized in tabular format by treatment groups (ie, migalastat-treated, ERT-treated, and untreated patients where appropriate). Enrollment summaries will also include a total summary column.

The precision of original measurements will be maintained in summaries, when possible. Means, medians, and standard deviations will be presented with an increased level of precision; means and medians will be presented to 1 more decimal place than the raw data, and the standard deviations will be presented to 2 more decimal places than the raw data.

Summaries of continuous variables that have some values recorded using approximate values (eg, < or >) will use imputed values. The approximate values will be imputed using the closest exact value for that measurement. For tables where rounding is required, rounding will be done to the nearest round-off unit. For example, if the round-off unit is the ones place (ie, integers), values \geq XX.5 will be rounded up to XX + 1 while values < XX.5 will be rounded down to XX.

Percentages will be based on available data and denominators will generally exclude missing values. For frequency counts of categorical variables, categories whose counts are zero will be displayed for the sake of completeness. For example, if none of the patients discontinue due to “lost to follow-up,” this reason will be included in the table with a count of 0. Categories with zero counts will not have zero percentages displayed.

Unless otherwise specified, percentages will be calculated based on the number of patients specified by the appropriate population definition.

7.2. Standard Calculations

Variables requiring calculation will be derived using the following formulas:

- Days – Durations, expressed in days between 1 date (date1) and another later date (date2), are calculated using the following formula:
$$\text{duration in days} = (\text{date2} - \text{date1}) + 1$$
- Weeks – Durations, expressed in weeks between 1 date (date1) and another later date (date2), are calculated using the following formula:
$$\text{duration in weeks} = (\text{date2} - \text{date1})/7$$
- Months – Durations, expressed in months between 1 date (date1) and another later date (date2), are calculated using the following formula:
$$\text{duration in months} = (\text{date2} - \text{date1})/30.4$$
- Years – Durations, expressed in years between 1 date (date1) and another later date (date2), are calculated using the following formula:
$$\text{duration in years} = (\text{date2} - \text{date1})/365.25$$
- Minutes – Durations, expressed in minutes between 1 time point (time1) and another later time point (time2), are calculated using the following formula:
$$\text{duration in minutes} = (\text{time2} - \text{time1})/60$$

- Age at time of diagnosis – The patient's age is calculated as the number of years from the patient's date of birth to the date of enrollment into the study if a date of birth is available:

$$\text{Age at time of diagnosis} = ([\text{Enrollment Date} - \text{Date of Birth}]/365.25)$$

- If only the year of birth is available, the age is calculated as follows:

$$\text{Age at time of diagnosis} = \text{Time of diagnosis Year} - \text{Birth Year}$$

- Age at Therapy Start – The patient's age is calculated as the number of years from the patient's date of birth to the date of migalastat or ERT therapy start if a date of birth is available:

$$\text{Age at Therapy Start} = ([\text{Therapy Start Date} - \text{Date of Birth}]/365.25)$$

- If only the year of birth is available, the age is calculated as follows:

$$\text{Age at Therapy Start} = \text{Therapy Start Year} - \text{Birth Year}$$

7.3. Statistical Reporting

Statistical analyses will be reported using summary tables, figures, and data listings. Continuous variables will be summarized with counts, means, standard deviations, medians, minimums, and maximums. Categorical variables will be summarized by counts and by percentage of patients. For event data, i.e., SAEs and the exposure-adjusted incidence rates will be summarized as

counts of patients with a new event per 1000 person-years exposure, with a 95% confidence interval (CI) using Ulm's method (Ulm 1990).

Recurrent events will be presented for SAEs and each specific FACE and will be shown as a total count of each event per 1000 person-years.

A Cox proportional hazards model will be used for the summary of time to event data.

Tables, listings, and figures will be presented in rich text file (RTF) format. Upon completion, all SAS programs will be validated by an independent programmer. In addition, all programmed outputs will undergo a senior level statistical review. The validation process will be used to confirm that statistically valid methods have been implemented and that all data manipulations and calculations are accurate. Checks will be made to ensure accuracy and consistency with this plan, consistency within tables, and consistency between tables and corresponding data listings. Upon completion of validation and quality review procedures, all documentation will be collected and filed by the project statistician or designee.

7.4. Dictionaries

The Medical Dictionary for Regulatory Activities (MedDRA®) will be used to code AEs, investigations, medical/ surgical procedure, indication and medical history for system organ class and preferred terms using Version 23.0 or the latest available version. The enhanced version of the World Health Organization Drug Dictionary (WHO-DRUG, latest available version) will be used to code all medications (prior and concomitant) to anatomical therapeutic chemical and preferred drug names.

8. PATIENT ACCOUNTING AND DISPOSITION

8.1. Patient Accounting

Patient enrollment will be tabulated by treatment group (migalastat, ERT, or untreated) and overall. The summary will include the number and percentage of patients in the Safety Population, the Primary and Secondary Effectiveness Populations.

8.2. Patient Disposition

Patient disposition will be summarized by treatment group and overall and at the time of diagnosis, at the start of treatment, and the time of treatment switch. Other time points will be investigated if needed. In addition, frequency counts and percentages of patients' reported reasons for lack of follow up data will be summarized by treatment group and overall. Disposition will be presented in the Safety Population, the Primary and Secondary Effectiveness Populations.

A patient listing will be presented to describe treatment switches patient study completion, reason for discontinuation, primary cause of death, and other reasons specified.

9. DEMOGRAPHIC AND OTHER CHARACTERISTICS

Demographic data, enrollment and treatment start characteristics, and medical history (Fabry disease history, FACEs history, and other medical history) will be summarized using descriptive statistics by treatment group at baseline. These summaries will be based on the Safety Population, and the Primary and Secondary Effectiveness Populations. Fabry disease history, cardiac event history, cerebrovascular event history, and renal event history will be summarized as presented on eCRFs; other medical history will be coded (Section [7.4](#)).

Those patients who are missing measurements of the variable being analyzed will not be included in the summary for that variable.

9.1. Demographics

Demographic variables collected prior to enrollment include date of birth, sex, race, and ethnicity. Age at baseline date of diagnosis for untreated patients and the date of start of the first treatment for treated patients), sex, race, ethnicity, pregnancy status for female patients and fertility status for male patients, will be summarized and reported.

For the Safety Population, data will be summarized at the time of diagnosis.

Age at the time of diagnosis (migalastat-treated versus untreated patients) and age at the start of the first treatment (migalastat-treated versus ERT-treated patients) will be analyzed as a continuous variable and will also be compared between groups using the categories: (< 12, 12 to < 18, 18 to < 65, \geq 65). Sex, ethnicity, and race will be analyzed as categorical variables.

Patient height and weight will be analyzed at the time of diagnosis and at the treatment start. Height and weight will be reported in metric units (height in cm and weight in kg) and will be analyzed as continuous variables.

9.2. Disease Characteristics

Documented variant of the gene encoding α -galactosidase A (*GLA*) will be presented as a summary and a listing.

Previous history of FACEs will also be summarized as both binary Yes/No variable and number and type of events.

Estimated GFR values will be summarized. eGFR values entered into eCRFs might have been measured by different methods. Therefore, they will be recalculated from creatinine to provide GFR_{CKD-EPI} values. eGFR_{CKD-EPI} values will be used to define categories for renal impairment.

Renal impairment will be categorized as Normal (GFR $>$ 90 mL/min/1.73 m²), Mild (GFR \geq 60 to 90 mL/min/1.73 m²), Moderate (GFR \geq 30 to 60 mL/min/1.73 m²), and Severe (GFR $<$ 30) and analyzed as a categorical variable.

9.2.1. Medical History

The following medical history collected at enrollment will be presented: history of diabetes, dyslipidemia, hypertension, and other medical history reported (coded as per Section [7.4](#)).

Duration of these diseases will also be presented for patients with a documented start and end date, and will be calculated as:

$$\text{End date} - \text{start date} + 1$$

Similarly, ECG results and ECHO collection (Yes/No) and overall interpretation (ie, normal, abnormal, not clinically significant, abnormal, potentially clinically significant) will be presented. Additionally, all available ECHO endpoints will be summarized.

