4. SAMPLE SIZE JUSTIFICATION

Approximately 115 patients with established Fabry Disease, estimated 2/3 female and 1/3 male.

Sample size was not determined statistically. All patients from Danish National Fabry Centre are included.

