- If start date is completely missing: start date will be imputed as 30 days past enrollment date.

- If (year is present and month and day are missing) or (year and day are present and month is missing): set month and day to the date of the first closest visit, unless another switch occurred before it. In such a case, set the start date to the date of the previous visit.
- If year and month are present and day is missing: set day to the first day of the month unless during that month there was a visit, in which case the day will be set to the day of that visit.

The following rules apply to end date of new or switched therapy:

- If end date is completely missing: end date will not be imputed unless there is another treatment switch. In that case, the end date is imputed as a day before that next treatment switch.
- If (year is present and month and day are missing) or (year and day are present and month is missing): set month and day to the date of the last visit in that year, unless another switch occurred. In such a case, set the end date to a day before that next treatment switch.
- If year and month are present and day is missing: set day to the date of the last day of the month.

Any partial dates will be displayed in data listings without and with imputation of missing days and/or months.

Concomitant Medications

The following rules apply to start date:

- If start date is completely missing: start date will not be imputed.
- If (year is present and month and day are missing) or (year and day are present and month is missing): set month and day to 1 January.
- If year and month are present and day is missing: set day to first day of the month.

The following rules apply to end date:

- If end date is completely missing: end date will not be imputed.
- If (year is present and month and day are missing) or (year and day are present and month is missing): set month and day to 31 December.
- If year and month are present and day is missing: set day to last day of the month.

Any partial dates will be displayed in data listings without imputation of missing days and/or months (eg, MAR2011, 2009). No other imputation of missing data will be performed.

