10. CONCOMITANT MEDICATIONS

Concomitant medications will be defined as medications taken on or after the date of enrollment into the study and through the duration of the study.

If the medication stop date is before the enrollment date, such a medication is considered a previous medication and will not be analyzed, with exception of the previous ERT therapy and the previous migalastat treatment but will be listed.

For prior ERT or migalastat therapy, an overall prior exposure table will be presented by treatment group at baseline. If the stop date is missing or therapy is continuing, the date to calculate prior exposure will be the study enrollment date. A data listing will include dose and infusion frequency.

Concomitant medications will be coded according to the WHO-DRUG and will be summarized by treatment group using the Effectiveness and Safety Populations.

All reports in this section will provide the number of patients who received a concomitant medication by preferred drug name, Anatomical Therapeutic Chemical (ATC) class, and overall. A patient who received multiple agents within an ATC class will only be counted once for that class. Similarly, a patient who received a drug multiple times will only be counted once for the preferred drug name. Patients will be accounted into the group at the time of concomitant medication start date.

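### The comorbidity duration summary in SAP 9.2.1 leaves out ongoing disease and describes only conditions that ended

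*SAP*

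**What the plan says.** SAP 9.2.1 first commits to showing the history itself: "The following medical history collected at enrollment will be presented: history of diabetes, dyslipidemia, hypertension, and other medical history reported". It then adds a second statistic: "Duration of these diseases will also be presented for patients with a documented start and end date". The formula is end date minus start date plus 1, with no alternative for a condition that has not ended.

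Three other places bear on the rule.

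- SAP 9, which governs these summaries by treatment group at baseline, says: "Those patients who are missing measurements of the variable being analyzed will not be included in the summary for that variable".
- SAP 6.1 gives date rules for SAEs and FACEs, Fabry therapy before enrollment, treatment switches and concomitant medications. It has none for medical history, and it closes with: "No other imputation of missing data will be performed".
- SAP 10, on prior ERT or migalastat exposure, does deal with a course that is still running: "If the stop date is missing or therapy is continuing, the date to calculate prior exposure will be the study enrollment date".

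**The concern.** Diabetes, hypertension and dyslipidemia are usually lifelong. Requiring an end date before a duration can be calculated selects the patients whose condition resolved, or was recorded as resolved. A mean or median from that subset does not describe how long affected patients have lived with the disease. It may also mislead, because it looks like an ordinary baseline characteristic by treatment group.

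What is at stake is limited but real. The study is not randomized, and its outcome is cardiac, renal and cerebrovascular events. The primary Cox model in SAP 13.1.1 does not adjust for these comorbidities, so the descriptive tables are where a reader would judge whether the groups differ on them. A duration figure shown there should be interpretable.

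**Working it through.** The plan states no numerical result on this point, so there is none to reproduce. The check is to follow one condition through the rules, then bound the loss.

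**Step 1. Apply the 9.2.1 rule.** Let S be the start date and E the end date. The plan gives duration = E − S + 1, only if both S and E are documented.

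| Condition at enrollment | S | E | Presence presented? | Duration presented? |
|---|---|---|---|---|
| Ended before enrollment, both dates known | yes | yes | yes | yes |
| Ongoing, start known | yes | none | yes | no |
| Ended, end date not recorded | yes | missing | yes | no |
| Start not recorded | missing | any | yes | no |

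The second row is the problem. The data needed for a baseline duration (S and the baseline date) are available, but the rule discards them.

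**Step 2. Look for a rule elsewhere that supplies E.** SAP 6.1 has no entry for medical history. Its closing sentence, "No other imputation of missing data will be performed", follows the concomitant medication rules and might be read as applying to those alone. On that narrower reading there is still no medical-history rule. SAP 9 confirms that a patient without a value drops out of the summary. Nothing restores the ongoing case.

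**Step 3. Compare with SAP 10.** For prior Fabry therapy, a missing stop date or a continuing course is cut at enrollment. SAP 11.1 defines enrollment as the date of the Fabry diagnosis. The same device would serve in 9.2.1 but is not used there.

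**Step 4. Bound the loss.** Let p be the share of affected patients whose condition is ongoing. The share contributing a duration is at most 1 − p, and lower if start dates or end dates of resolved conditions are missing. The documents do not give p. For illustration only:

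| p (assumed) | 1 − p, largest share contributing |
|---|---|
| 50% | 50% |
| 80% | 20% |
| 95% | 5% |

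Whatever the value of p, every contributing condition is one that ended.

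**Step 5. Trace where duration is used.** Comorbidity duration is not among the covariates of the primary Cox model (SAP 13.1.1), the eGFR model (SAP 13.7) or the survival model (SAP 15.4). It is not a subgroup in SAP 12. It appears only in the descriptive summary.

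**The case against.** The strongest reply is that 9.2.1 is open about its limits. It names the subset it uses, and SAP 9 says that patients without a value are excluded. A careful reader would not take the figure for all affected patients, and nothing inferential depends on it. All of that is correct, and it is why the point is minor. It does not make the figure useful, because a stated restriction that selects resolved disease still yields an unrepresentative summary.

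Four stronger readings are tempting and are not supported.

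- *Ongoing disease disappears from the baseline table.* It does not. The history of each condition is presented with no date requirement; only the added duration statistic omits it.
- *The treatment groups cannot be compared on comorbidity.* They can be compared on presence. Only the comparison of duration is impaired.
- *Nearly all affected patients are lost.* That ongoing disease is the usual case is a reasonable inference from the chronic nature of these conditions, but no document gives a proportion. Any percentage lost is just the complement of an assumed one.
- *Follow-up time will leak into a baseline figure.* The formula does not cap an end date at enrollment, so this is possible. However, 9.2.1 concerns history collected at enrollment, and on that reading a later end date should not normally occur. The protocol's plan to record comorbidities at treatment start and switch where possible (Other measures) leaves some room for it, but nothing shows that it happens.

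A practical objection also stands. The protocol's variable tables list no onset or end dates for these conditions, so missing start dates may limit the table whatever rule is adopted.

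**Conclusion.** The point holds for the duration summary alone. As written, SAP 9.2.1 yields durations only for conditions that ended, and no other section corrects this. It is a wrong derivation rule rather than a missing detail, since the text states who is included and that rule excludes ongoing disease.

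The share of affected patients left out is at least the share with ongoing disease, which the documents do not report. The conclusion that the remaining subset is unrepresentative rests on these conditions being mostly chronic; that is an inference and is not documented in the plan.

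No effect estimate, test, model or primary conclusion would change. This is a low-priority improvement to a descriptive table.

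**What to change.** Replace the 9.2.1 rule with a duration at baseline:

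duration = min(end date, enrollment date) − start date + 1

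For a condition recorded as ongoing, the enrollment date is used. This follows the approach SAP 10 takes for continuing therapy, and it also removes any doubt about end dates after enrollment.

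Enrollment (diagnosis) should be the default cut-off, rather than the Analysis Start Date. SAP 11.2 defines two Analysis Start Dates: diagnosis for migalastat versus untreated, and treatment start for migalastat versus ERT. A migalastat patient could then have two durations under one label. SAP 9.1 also summarizes the Safety Population at diagnosis. Where a table takes treatment start as its baseline, cut at that date and say so in the table title.

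Report beside each duration the number of conditions ongoing and the number with a missing start date. Count a missing end date with no record that the condition is ongoing separately, so that it is not silently treated as ongoing.

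The cost is a short change to the SAP text and a little more derivation work. Ongoing cases need a start date, which the present rule already requires, and a record that the condition is ongoing. The table will still be only as complete as the recorded start dates.

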10. CONCOMITANT MEDICATIONS

Concomitant medications will be defined as medications taken on or after the date of enrollment into the study and through the duration of the study.

If the medication stop date is before the enrollment date, such a medication is considered a previous medication and will not be analyzed, with exception of the previous ERT therapy and the previous migalastat treatment but will be listed.

For prior ERT or migalastat therapy, an overall prior exposure table will be presented by treatment group at baseline. If the stop date is missing or therapy is continuing, the date to calculate prior exposure will be the study enrollment date. A data listing will include dose and infusion frequency.

Concomitant medications will be coded according to the WHO-DRUG and will be summarized by treatment group using the Effectiveness and Safety Populations.

All reports in this section will provide the number of patients who received a concomitant medication by preferred drug name, Anatomical Therapeutic Chemical (ATC) class, and overall. A patient who received multiple agents within an ATC class will only be counted once for that class. Similarly, a patient who received a drug multiple times will only be counted once for the preferred drug name. Patients will be accounted into the group at the time of concomitant medication start date.

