#### Variables concerning concomitant medication

The included concomitant medication to be recorded is restricted to medications believed to be of clinical interest. Medication will be recorded as to their use at inclusion and regarding their change throughout the study if possible.

Concomitant medication at inclusion	
ACE-I/ ARB	Yes No
Beta-blocker	Yes No
Ca-blockers	Yes No

Diuretics	Yes No
Statins	Yes No

Date (Date)	Drug (Name)	Action* (Categorical)	Dose (Integer)	Dose interval (Comment)	Comment (Comment)
----------------	----------------	--------------------------	-------------------	----------------------------	----------------------

\*Action is restricted to four levels: Initiation, decrease, increase, cessation.

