2. OVERVIEW OF STUDY DESIGN

This is a retrospective study of prospectively collected patient data with the use of secondary patient data from both paper and electronic patient files. All patients are treatment naïve at time of diagnosis. Both migalastat and ERT will be studied retrospectively. Also untreated patients will be studied by assessment of relevant clinical and laboratory variables. The analysis will originate at the time of diagnosis.

The patients have been followed for more than 20 years from 2001 until December 2023. All identified patients with Fabry disease, whether receiving specific Fabry medication or not, have been offered annual or biannual thorough workups including examinations of Fabry associated organ function and symptoms. The study will be carried out at the Danish National Fabry Centre, Department of Endocrinology, Copenhagen University Hospital.

All patients from the Danish National Fabry Centre will be included. Subgrouping is aimed at depending on available numbers: non-amenable, amenable, classic, non-classic, males, females, treated including type of treatment or untreated.

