15.1. Approach to Safety Analyses

As this is an observational study, patients may switch or stop therapies. In the Safety Population, analysis will present results based on the actual exposure, ie, treatment group at the time of the event (migalastat, ERT, or untreated). As patients can stop or switch therapy while enrolled in the study, they might be counted more than once in the analysis.

Serious adverse events will be analysed as described in Section 13 for the composite FACES.

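### The concomitant medication table counts a drug only in the treatment group in force when it started, so long-term drugs carried into ERT or migalastat are left out of those groups

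*SAP*

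**What the plan says.** SAP section 10 sets the scope: "Concomitant medications will be defined as medications taken on or after the date of enrollment into the study and through the duration of the study". A drug begun earlier and still in use at enrollment is therefore included. The coded drugs "will be summarized by treatment group using the Effectiveness and Safety Populations", as numbers of patients receiving each drug and each ATC class. Two counting rules follow. On repeat use, "a patient who received a drug multiple times will only be counted once for the preferred drug name". On the choice of column, "Patients will be accounted into the group at the time of concomitant medication start date". Nothing in section 10 or elsewhere counts an ongoing drug again when Fabry treatment starts or changes.

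The design makes this matter. SAP section 2 states: "All patients are treatment naïve at time of diagnosis". SAP 11.1 sets enrollment equal to the diagnosis date, and SAP 6.1 accepts several therapy changes over the 20 years.

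On the data, the protocol (Variables concerning concomitant medication) says: "Medication will be recorded as to their use at inclusion and regarding their change throughout the study if possible". It provides a Yes/No form at inclusion for five drug classes (ACE-I/ARB, beta-blockers, calcium blockers, diuretics, statins) and a dated log of initiation, increase, decrease and cessation. For these drugs SAP 6.1 says: "If start date is completely missing: start date will not be imputed".

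**The concern.** The table is meant to show what patients received in each group, but the rule shows where each drug was begun. For short courses the two nearly coincide. For drugs taken for years, such as ACE-I/ARB, beta-blockers, statins and diuretics, they can differ widely.

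The comparison of migalastat, ERT and untreated patients is not randomized, and none of the planned models adjusts for these drugs. A reader who wants to know whether a difference in FACEs, eGFR or albuminuria could reflect background cardio-renal therapy will look at this table. As specified, it could show low use in a treated group simply because the drugs were already established when that group was entered.

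**Working it through.** The plan attaches no figure to this table, so there is nothing to reproduce. The check has two parts.

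**1. Following the rule through the design**

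- Drug begun before diagnosis and continued: all patients are treatment naïve then, so its natural column is untreated, although the SAP does not say so. It is never counted under ERT or migalastat.
- Drug begun while untreated and continued on therapy: counted under untreated only.
- Drug begun on ERT and continued after a switch to migalastat: counted under ERT only.
- Drug stopped and restarted on therapy: it may carry a new start date, but section 10 does not say whether counting once means once per group or once overall.
- Partial start dates: SAP 6.1 moves them to 1 January or to the first of the month. In the year or month of a treatment start, this can push a drug into the earlier group.

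**2. Size, as an illustration**

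All inputs are assumptions, since the documents give none. The drug is never stopped.

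- p0 = share already on the drug at diagnosis: 0, 0.1, 0.3
- λ = new starts per year among non-users: 0.02, 0.05
- u = years before the therapy period: 0.25, 2, 5, 10
- T = years in the therapy period: 5

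Formulas:

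- Users during therapy = 1 − (1 − p0)·exp(−λ(u + T))
- Counted in the therapy group by start date = (1 − p0)·exp(−λu)·(1 − exp(−λT))
- Missed share = 1 − counted / users

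One case in full, with p0 = 0, λ = 0.05, u = 5:

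- Users = 1 − exp(−0.5) = 0.393
- Counted = exp(−0.25)·(1 − exp(−0.25)) = 0.172
- Missed = 1 − 0.172/0.393 = 0.56

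| p0 | λ | u | Users on therapy | Counted | Missed share |
|---|---|---|---|---|---|
| 0 | 0.02 | 0.25 | 10.0% | 9.5% | 5% |
| 0 | 0.05 | 2 | 29.5% | 20.0% | 32% |
| 0 | 0.05 | 5 | 39.3% | 17.2% | 56% |
| 0.1 | 0.05 | 0.25 | 30.8% | 19.7% | 36% |
| 0.1 | 0.05 | 5 | 45.4% | 15.5% | 66% |
| 0.3 | 0.02 | 10 | 48.1% | 5.5% | 89% |

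Over the whole grid the missed share runs from 5% to 89%. It rises with use at diagnosis and with time before the therapy period. The 5% occurs only with p0 = 0 and u = 0.25. SAP 5.1 and 5.2.1 treat patients who start therapy within 3 months of enrollment as initially in that therapy group. If that rule is applied to this table, the missed share in the 5% case falls to zero. It does not help for drugs begun before enrollment. Stopping of drugs, which the model leaves out, would generally lower the missed share.

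**The case against.** Much can fairly be said on the other side.

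- **No estimate moves.** Concomitant medication is not a covariate in the Cox model (SAP 13.1.1), the eGFR MMRM (13.7) or the survival model (15.4). This stands. A reader might infer that the hazard ratio is biased by the rule, but the documents do not support that.
- **The data survive.** Start and stop dates are collected and SAP 6.1 refers to listings, so overlap can be rebuilt. This stands, and it is why the fix is cheap.
- **Other tables help.** Hypertension, dyslipidemia, diabetes and FACE history are summarized at baseline (SAP 9). They inform comparability but do not show treatment received.
- **There is no conflict with SAP 15.1.** A reader might see one with its actual-exposure approach. That section concerns safety results and places an event in the group in force when it occurs, which is the same kind of convention as placing a drug by its start. It sets no overlap rule for medication.
- **The direction for migalastat is not established.** It is tempting to say that migalastat comes last and so loses most. The documents give no treatment sequences, and SAP 12 plans a subgroup of treatment-naïve migalastat patients. With an assumed 5 years untreated, 9 on ERT and 6 on migalastat, and a uniformly timed start, true use would be 25%, 70% and 100% against 25%, 45% and 30% counted, a 3.3-fold shortfall on migalastat. That is one invented course, not a property of this study. Even there the untreated count is correct.
- **Drugs begun before diagnosis are not left without a possible group.** They fall naturally under untreated. Only the wording, and the handling of undated drugs, is missing. The dated log makes undated-only drugs a residual of unknown size.

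**Conclusion.** The concern holds for the descriptive by-group table. The stated rule leaves a continuing drug out of every treatment group entered after it was begun, and no other section corrects this. That is a rule giving wrong counts, not a missing detail. The reading of the rule is firm. The size is not: about 5% to 89% of users on therapy missed, under assumed usage rates, an assumed time before therapy, a 5-year therapy period and no stopping. The consequence is limited to the comparison of background medication between groups. The sentence should be corrected before the tables are programmed.

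**What to change.** Replace the assignment sentence in SAP section 10 with wording such as:

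> A patient is counted once per drug and once per ATC class in every treatment period (migalastat, ERT, untreated) that the medication's start–stop interval overlaps. Drugs started before enrollment and ongoing are counted as untreated at enrollment and in each later period they are documented to overlap.

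Add a table of medications ongoing at each Analysis Start Date and each switch date.

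Show drugs marked Yes on the inclusion form with no later record as use at enrollment only, flagged as unknown afterwards. They should not be carried forward until a recorded cessation. The protocol records changes only where possible, so unrecorded stops would inflate later use, and SAP 6.1 rules out further imputation. As 6.1 also leaves a completely missing stop date unimputed, add a line saying how a logged drug with no recorded cessation is read.

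The cost is a few sentences and a date-overlap join in programming, with no new data. Patients can then appear in more than one column, which the SAP already accepts for safety results. Any-overlap counts rise with the length of a period; the table of drugs ongoing at each start date offsets this.
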